Brief Summary	
This study is a prospective randomized trial examining the effect of tranexamic acid (TXA) and aminocaproic acid (ϵ-Ahx) with local anesthetics and thrombin in all electively created surgical wound beds in hand surgery to provide long term pain relief and decrease the use of postoperative narcotics.
 
All surgical created wounds for any hand surgery will be treated in a randomized fashion with the following four arms:
 
1. Bupivacaine + lidocaine2. Bupivacaine + lidocaine + thrombin3. Bupivacaine + lidocaine + thrombin + tranexamic acid4. Bupivacaine + lidocaine + thrombin + aminocaproic acid 
All are applied topically to surgical bed prior to closure of skin.

Phase	N/A
Objectives	
The primary objective of this study is to evaluate the effectiveness of topical antifibrinolytics, thrombin and local anesthetics on postoperative pain control in patients undergoing elective hand surgery. We want to determine the efficacy of this treatment over treatment with thrombin and local anesthetics and just local anesthetics alone to the same population of patients.
 
The secondary objective of the study is to reduce the amount of opioid pain medications required postoperatively for routine hand surgery procedures.

Methodology	Prospective single blinded study
Endpoint	Degree of pain and amount of adjuvant pain medication used at 1 month post surgery
Study Duration	12 months
Participant Duration	Pre-operative visit occurs up to 3 months prior to surgery Final Study visit occurs up to 6 weeks after surgery. Primary endpoint (returning completed pain diary to study staff) occurs at Day 14. Participants remain enrolled in the study up until their standard of care post-op visit, which typically occurs 4-6 weeks after surgery. Participation is complete when participants complete their final standard of care post-op visit.
Duration of IP administration	Applied topically to surgical bed prior to closure of skin
Population	Nontraumatic, elective upper extremity (hand) surgery cases, age 18 or older
Study Sites	NYU Langone Health Bellevue Hospital Center
Number of participants	40 (10 per study arm)
Description of Study Agent/Procedure	Applied topically to surgical bed prior to closure of skin: 1. Bupivacaine + lidocaine (reference therapy) 2. Bupivacaine + lidocaine + thrombin 3. Bupivacaine + lidocaine + thrombin + tranexamic acid 4. Bupivacaine + lidocaine + thrombin + aminocaproic acid

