Reference Therapy	All study agents have been used as standard of care

CONFIDENTIAL

This material is the property of the NYU School of Medicine and Langone Medical Center. Do not disclose or use except as authorized in writing by the study sponsor
Interventional Template Version: 11 January 2019

Statistical Analysis	To evaluate PACU time as a function of each group, a one way analysis of variance test followed by a Tukey-Kramer post hoc test will be performed. To assess the number of pain pills need as a function of each group, a Kruskal-Wallis test followed by a Dunn post hoc analysis will be performed.
----------------------	---

Schematic of Study Design

Screening/Baseline Visit (up to 3 months prior to day of surgery)

1. Obtain informed consent of potential participant verified by signature on written informed consent for screening form.
2. Review medical history to determine eligibility based on inclusion/exclusion criteria.
3. Review medications history to determine eligibility based on inclusion/exclusion criteria.
4. Perform medical examinations needed to determine eligibility based on inclusion/exclusion criteria.
5. Schedule day of surgery where primary intervention will be performed.
6. Provide participants with information regarding tranexamic acid, and operative steps for administration of drugs into surgical wound prior to closure.
7. Provide participants with log books.
8. Randomize patient using sealed envelope method.

Day of Surgery

1. Verify patient still meets inclusion/exclusion criteria.
2. Administer study treatment
3. Patient fills out Day 1 of pain diary

Intermediate Visits

1. Participants will be called via phone each day by the study team to ensure they have completed their daily log of numerical pain rating scale and number of pain pills taken.
2. They will arrive for an intermediate visit on their first postoperative visit (variable time, between 3-14 days postoperatively). Log books will be collected only after postoperative day 14.

Final Study Visit (up to 6 weeks post surgery)

Pain logs will be collected from participants who have not already returned them to study staff. The participants will be released of their duties to the study once the log books have been returned to the physicians. They will continue their routine follow up per the follow up schedule for each hand surgery procedure. No additional data is collected for study purposes at post-op visits beyond data collected per standard of care.

CONFIDENTIAL

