2.2.1 Clinical Data to Date

Tranexamic acid is a synthetic derivative of the amino acid lysine. Its mechanism of action is via inhibition of fibrinolysis by blocking the lysine binding site on plasminogen. It acts as a competitive inhibitor of conversion of plasminogen to plasmin and at higher concentrations a non-competitive inhibitor of plasmin.

Thrombin is a serine protease coagulant that both converts soluble fibrinogen into insoluble fibrin strands and activates factor XIII to catalyze covalent crosslinking of these strands, thereby forming a stable fibrin clot. It also promotes platelet aggregation at the site of vascular injury, via the activation of specific protease-activated receptors. Thus, exogenous topical thrombin directly activates the terminal stages of blood clot formation at the site of application.

Bupivacaine is an amino-amide local anesthetic. Onset of action is 1-17 min. Duration of action (route and dose-dependent) 2-9 hr. Half life: neonates 8.1 hours, adults: 2.7 hours. Time to peak plasma concentration (for peripheral, epidural, or caudal block): 30-45 min. Protein binding: about 95%. Metabolism: hepatic. Excretion: renal (6% unchanged).

Lidocaine is an amino-amide local anesthetic. Onset of action is 2-4 min. Duration of action (route and dose-dependent) 2 - 3.5 hr. Half life: 1.5-2 hr. Protein binding: 60-80%. Metabolism: hepatic. Excretion: renal.

Previous work by our group showed that the addition of topical thrombin to local anesthetic at the end of elective hand surgery provides for sustained postoperative pain control. Patients in that study who received thrombin and local anesthetic before wound closure had lower pain levels and were discharged from the PACU sooner than those who received local anesthetic alone. We hypothesize that the addition of a topical antifibrinolytic agent such as tranexamic acid with thrombin and local anesthetic at the end of elective hand surgery will provide even greater pain relief through the formation of a stable clot that prolongs the effect of local anesthesia. We hypothesize we will see even lower pain scores and lower number of pain pills and shorter PACU times in the postoperative period in the groups with a tranexamic acid + thrombin + local anesthetic than the groups with just thrombin + local anesthetic.

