3.1 Primary Objective

The primary objective of this study is to evaluate the effectiveness of topical antifibrinolytics, thrombin and local anesthetics on postoperative pain control in patients undergoing elective hand surgery. We want to determine the efficacy of this treatment over treatment with thrombin and local anesthetics and just local anesthetics alone to the same population of patients.

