4.2 Study Endpoints

4.2.1 Primary Study Endpoints

Comparison of pain levels using a visual analog scale preoperatively and postoperatively

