10.1.2 Analysis of the Primary Efficacy Endpoint(s)

Data will be expressed either as a mean (SD) or median and interquartile range (IQR). To evaluate PACU time as a function of each group, a one way analysis of variance test followed by a Tukey-Kramer post hoc test will be performed. To assess the number of pain pills need as a function of each group, a Kruskal-Wallis test followed by a Dunn post hoc analysis will be performed. To compare pain levels between the treatment arms, pain scores on a scale of 1 (lowest aka no pain) to 10 (highest pain experienced in life) will be collected daily via a patient log. They will be analyzed as a change from baseline (preoperative) pain levels and analyzed used a series of two proportion z tests with a family error rate equal to 0.05. For all tests, a P value of less than 0.05 will be considered statistically significant.

Pain is a subjective measure. We will be using an analog pain scale and reference them to the patients pre and postoperatively to account for this. Patients may take over the counter pain medication postoperatively. We cannot control the patient's use of over the counter pain medications while at home, thus we will have to rely on their accuracy and honesty for this study.

Patients will be called daily to ensure completion of daily log books. If they are not able to do this, they will be removed from the study analysis. If the patients return to clinic at 4-6 weeks post-surgery and they have completed their logs, their data will still be accepted. But if there is missing data, they will be removed from the analysis.

11 Source Documents and Access to Source Data/Documents

All data will be stored on HIPAA compliant and encrypted REDCap, approved by the institution and managed by MCIT.

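### The primary pain endpoint, a change in a numeric score, is assigned two-proportion z tests with no proportion defined; the comparisons, diary day and adjustment method are also left open

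*Combined protocol and SAP*

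**What the plan says.** Section 4.2.1 gives the primary endpoint as "Comparison of pain levels using a visual analog scale preoperatively and postoperatively". Section 10.1.2 describes the data as "pain scores on a scale of 1 (lowest aka no pain) to 10 (highest pain experienced in life", collected daily in a patient log, and then gives the analysis: "They will be analyzed as a change from baseline (preoperative) pain levels and analyzed used a series of two proportion z tests". It sets a family error rate of 0.05 for that series and ends: "For all tests, a P value of less than 0.05 will be considered statistically significant".

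The same section treats the secondary endpoints more fully. PACU time has one-way ANOVA with Tukey-Kramer, and pill counts have Kruskal-Wallis with Dunn. The Statistical Analysis row of the Protocol Summary repeats those two ("To evaluate PACU time as a function of each group, a one way analysis of variance test followed by a Tukey-Kramer post hoc test" for PACU time) and gives no analysis of pain.

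On what is to be compared, section 3.1 says "We want to determine the efficacy of this treatment over treatment with thrombin and local anesthetics and just local anesthetics alone". Section 2.2.1 states a narrower hypothesis for the tranexamic acid arm against the thrombin arm: "We hypothesize we will see even lower pain scores and lower number of pain pills and shorter PACU times in the postoperative period". On timing, the Endpoint row of the Protocol Summary reads "Degree of pain and amount of adjuvant pain medication used at 1 month post surgery", while sections 4.1 and 7.1.1 run the pain scores to postoperative day 14.

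**The concern.** The test and the variable do not match. To apply a two-proportion z test, someone must first turn each patient's change in score into a yes or no, and the plan does not say how. That choice, the diary day, the preoperative score used as baseline, the list of comparisons and the adjustment could all be made after the data are seen. With 10 patients per arm, the cut alone can move power from moderate to very low for the same true effect. Whatever result is reported for the primary endpoint would then rest on an analysis that was not fixed in advance.

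**Working it through.** **1. Is a proportion defined anywhere?** Sections 3.1, 4.1, 4.2.1, 7.1.1 and 10.1.2 and the Protocol Summary all speak of pain levels, scores or differences in scores. None defines a responder, a threshold or a percentage. No other test of pain is given.

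**2. What is fixed and what is open?**
- Stated: the type of test and the family error rate of 0.05.
- Comparisons not listed: section 3.1 suggests each antifibrinolytic arm against arms 2 and 1 (2 × 2 = 4); section 2.2.1 suggests one; each arm against arm 1 would be 3; all pairs of four arms would be 6. If all 14 diary days were tested, six pairs would become 6 × 14 = 84.
- Adjustment not named. The closing P < 0.05 rule agrees with the family rate only if P means adjusted P, which is not said.

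**3. Time point, baseline, scale.**
- Time: 1 month in the Endpoint row; 14 days in sections 4.1 and 7.1.1. The Participant Duration row and section 5.5 place a primary endpoint at Day 14 but describe it as return of the diary. Section 7.2 plans no study data at later visits beyond standard of care, so no diary score exists at 1 month.
- Baseline: section 7.1.1 takes one preoperative score at the clinic visit and another in the holding area, the latter labelled POD#0. Section 10.1.2 does not say which is the baseline.
- Scale: section 7.1.1 gives 0–10 in one place and 1–10 in another; section 10.1.2 gives 1–10.

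**4. What the choice of cut does to power.** The plan gives no effect size, SD or power, so its figure of 10 per arm cannot be reproduced. Assumptions: 10 per arm, normal scores with common SD, two-sided tests, and a true shift of d = 1.32 SD, chosen only because it gives a t test 80% power.

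Noncentrality = d × √(n/2) = 1.32 × √5 = 2.95.
- One t test, 18 df, critical value 2.10: power 79.7%.
- All six pairs by Tukey, 36 df, critical value 3.81/√2 = 2.69: power for one pair 60%.
- For comparison, Bonferroni at 0.05/6 with 36 df, critical value 2.79: 57%.

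For the z test, the shares above a cut follow from the normal distribution, and power comes from enumerating all 11 × 11 outcomes for two arms of 10. Pooled z = (x − y)/10 ÷ √(p̄(1 − p̄) × 2/10), with p̄ = (x + y)/20. The unpooled version uses the two separate variances, and unequal proportions with zero standard error count as significant.

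| Cut | Shares | Pooled z, 0.05 | Unpooled z, 0.05 | Pooled z, 0.05/6 |
|---|---|---|---|---|
| Midway between the arms | 25.5% vs 74.5% | 60.0% | 70.7% | 39.6% |
| At one arm's mean | 50% vs 90.7% | 49.0% | 66.6% | 21.8% |
| 0.5 SD beyond it | 69.1% vs 96.6% | 27.7% | 49.5% | 4.1% |

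So one test loses 80 − 60 = 20 to 80 − 28 = 52 percentage points with the pooled z test. Over six pairs the numeric analysis has about 60% against 40/22/4%. Little of that gap comes from Tukey rather than Bonferroni (60% against 57%).

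**The case against.** The best defence is that this is loose drafting and not an impossible analysis. The test type and the 0.05 family rate are named, and a two-proportion test could be run on, for example, the share of patients who improved from baseline. That is right as far as it goes, so it would be too strong to infer that no test is named or that nothing could be computed. But that share appears nowhere in the plan, and choosing it later is the problem.

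Some stronger readings are not supported:
- *The trial will test without adjustment.* Raw P < 0.05 over six pairs on one day would give a family error of about 4/15/18% (pooled) or 19/32/29% (unpooled) at assumed responder rates of 10/30/50%. Section 10.1.2 states a family rate of 0.05, so those figures apply only if that statement is ignored. The closing sentence is ambiguous; it is not a plan for raw testing.
- *The documents give several clashing time points.* The 14-day statements agree with each other. Only the 1-month row is out of line, and the Day 14 entry in section 5.5 concerns return of the diary.
- *The holding-area score is plainly the baseline because it is more recent.* Its POD#0 label, and section 7.2 calling the earlier visit the baseline visit, point the other way. The documents leave this open.
- *The unpooled z test avoids the loss.* With Bonferroni over six pairs its power is 46/39/13%, and its family error at responder rates of 10/30/50% is 0.5/9.9/8.5%, so it does not reliably hold 0.05. The pooled version gives 0.0/3.0/5.8%.

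The power figures also rest on an assumed effect and normal scores; bounded whole-number scores could change the gap. The finding itself rests on the text.

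**Conclusion.** The concern holds. The only analysis given for the primary endpoint does not fit the variable, and it can be run only after a dichotomy that the plan does not define. The comparisons, diary day or days and adjustment method are missing; the 1-month row disagrees with the 14-day diary; the baseline score and the scale are not settled. Under the stated assumptions (1.32 SD, normal scores, exactly 10 evaluable per arm), one test falls from 80% power to 60/49/28% pooled or 71/67/50% unpooled. With six pairs at a nominal family rate of 0.05, the comparison is about 60% for Tukey against 40/22/4% for the pooled z test. These sizes are illustrations, since the plan gives no effect size. The correction should be made before any outcome data are examined, because it concerns the primary endpoint.

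**What to change.** In section 10.1.2, replace the z-test sentence with one primary analysis that keeps the score numeric: a linear model of one prespecified pain summary within days 0–14, with arm as a factor and one named preoperative score as covariate. The sponsor should choose the summary in advance; the day-14 score and the mean of the daily diary scores are both possible.

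List the comparisons: either all six pairs with Tukey-Kramer, which is already planned for PACU time, or the contrasts implied by section 3.1 with Holm. State that adjusted P values are compared with 0.05. Add Kruskal-Wallis with Dunn on the change in the same summary as a sensitivity analysis.

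Correct the 1-month entry in the Protocol Summary to match the 14-day diary, state which preoperative score is the baseline, and use one pain scale throughout, including the visual analog wording in section 4.2.1 where sections 4.1 and 7.1.1 refer to a numerical rating scale.

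The cost is protocol and SAP wording, with no new data or patients. That holds for the 14-day choice; keeping 1 month would need pain scores that the schedule does not plan.

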4.1 Description of Study Design

The study is a single blinded placebo-controlled prospective randomized controlled trial. Patients will be randomized into one of four groups:

1. Topical lidocaine and bupivacaine alone
2. Topical lidocaine and bupivacaine with thrombin
3. Topical lidocaine and bupivacaine with thrombin and tranexamic acid

CONFIDENTIAL

This material is the property of the NYU School of Medicine and Langone Medical Center. Do not disclose or use except as authorized in writing by the study sponsor
Interventional Template Version: 11 January 2019

4. Topical lidocaine and bupivacaine with thrombin and aminocaproic acid

Patients meeting inclusion criteria will be randomized at their preoperative appointments and an initial evaluation will be completed for pre-operative pain levels using the numerical pain rating scale. At the conclusion of their respective surgery just prior to wound closure, the appropriate medications will be topically administered into the wound and the wound will be closed via standard method. Patients will record pain scores at home daily and also record the amount of pain pills needed postoperatively until post operative day 14. Analysis will be completed to ascertain the difference between preoperative and postoperative scales after 14 days among the four groups. We will also analyze the differences in the amount of opioid pain pills needed postoperatively among the four study groups.

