- The patients will be counseled on the study objectives and methods of data collection. The numerical pain rating scale will be explained in detail to the patient.
- The patients will be administered a pain diary in which they will be able to log their daily pain level at the same time each day (AM) based on the numeric pain scale (1-10). They will also be instructed to log their pain medication usage and the number of pills of Norco 5/325 mg that are consumed. This log will continue daily for a total of 14 days postoperatively.

The first visit will be the initial evaluation of the patient when they present for their individual hand surgery evaluation. If they qualify for their study, an initial preoperative pain scale will be used to assess their pain level.

The next assessment will be on the day of surgery. The patient will be evaluated in the preoperative holding area and another pain level evaluation will be done for a POD#0 timepoint.

The patient will be evaluated in PACU for total time in PACU.

Each patient will receive their log book and take it home with them. The patients will be called on each day by the study team to ensure that they have been logging their daily pain score. The study team will call the patient for this purpose.

The patients will be seen in person on their first postoperative visit (approximately 1-2 weeks later). If this is prior to postoperative day 14, they will follow up again in hand clinic after day 14 (in 4-6 weeks post-surgery) to submit their log books.

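### Pain is analysed as an unadjusted change from the pre-operative score, which can cost precision on the primary endpoint; the size of the loss depends on SDs and a correlation the plan does not give

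*Combined protocol and SAP*

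**What the plan says.** The primary endpoint in section 4.2.1 is "Comparison of pain levels using a visual analog scale preoperatively and postoperatively", with no time point or summary measure fixed. Section 10.1.2 then states how the scores are handled: "They will be analyzed as a change from baseline (preoperative) pain levels". The same sentence names the test: the changes are "analyzed used a series of two proportion z tests with a family error rate equal to 0.05". No cut-off is given that would turn a change in pain into a proportion. The reason offered for using the pre-operative score is that pain is subjective: "We will be using an analog pain scale and reference them to the patients pre and postoperatively to account for this". Section 4.1 describes the same contrast: "Analysis will be completed to ascertain the difference between preoperative and postoperative scales after 14 days among the four groups".

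No section plans an analysis that adjusts for the pre-operative score as a covariate. Two such scores are collected. Section 7.1.1 has one at the first visit ("If they qualify for their study, an initial preoperative pain scale will be used to assess their pain level") and a second shortly before the operation ("The patient will be evaluated in the preoperative holding area and another pain level evaluation will be done for a POD#0 timepoint"). Section 10.1.2 does not say which of them is the baseline.

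**The concern.** Subtracting the pre-operative score assumes that each extra point of pain before surgery carries through as one extra point afterwards, that is, a baseline slope of 1. There is reason to doubt this here. The earlier score reflects the underlying hand condition and may be taken up to 3 months before surgery. The outcome is pain from a fresh surgical wound, with an opioid prescribed and over-the-counter analgesics uncontrolled. If the slope is well below 1, subtraction adds baseline noise to the outcome and over-corrects any chance baseline difference between arms.

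The trial has little room for avoidable noise. It has 10 patients per arm, no enrolment allowance for losses (section 5.6), and drops patients with incomplete diaries (section 10.1.2). The score needed for a more precise analysis is already collected.

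**Working it through.** **Inputs from the documents.** Four arms of 10 (section 10.1.1). Family error rate 0.05 for the pain tests (section 10.1.2). Sidedness is not stated; two-sided is assumed. No SD, pre/post correlation, effect size, response rate or target power is given.

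**Assumed inputs.** Notation: ρ is the pre/post correlation and k = SD_pre/SD_post. The true difference is 1.3 SD of the post-operative score, and variances are equal across arms.

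**1. The plan's own figure.** Ten per arm cannot be reproduced, because its inputs are missing. Solving backwards with the normal approximation, 10 per arm gives 80% power for √(2/10) × (1.960 + 0.842) = 1.253 SD on a continuous outcome, for one pair at two-sided 0.05. The 1.3 SD used below is close to that value; it has no source in the documents.

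**2. Variances, in units of the post-operative variance.**
- Post-operative score alone: 1
- Change from baseline: 1 + k² − 2ρk
- Baseline-adjusted (ANCOVA): 1 − ρ²

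Change is noisier than the post-operative score alone when k² > 2ρk, that is, when ρ < k/2. The break-even correlation is 0.25, 0.375, 0.5, 0.625 and 0.75 at k = 0.5, 0.75, 1, 1.25 and 1.5.

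Change minus ANCOVA is (1 + k² − 2ρk) − (1 − ρ²) = (k − ρ)². This is never negative and is zero only when ρ = k, where the baseline slope ρ/k equals 1. ANCOVA costs one error degree of freedom.

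**3. Illustrative power for a comparison of means.** One pair, two-sided 0.05, noncentral t with noncentrality 1.3/√(V × 2/10), where V is the variance from step 2. Degrees of freedom are 40 − 4 = 36 for change and 35 for ANCOVA. For example, with k = 1 and ρ = 0.3, change has V = 1 + 1 − 0.6 = 1.40 and noncentrality 1.3/√0.28 = 2.457. ANCOVA has V = 0.91 and noncentrality 1.3/√0.182 = 3.047.

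At ρ = 0.3:

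| k | Break-even ρ | V, change | V, ANCOVA | Ratio | Power, change | Power, ANCOVA |
|---|---|---|---|---|---|---|
| 0.5 | 0.25 | 0.95 | 0.91 | 1.04 | 82.7% | 84.2% |
| 1 | 0.5 | 1.40 | 0.91 | 1.54 | 66.7% | 84.2% |
| 1.5 | 0.75 | 2.35 | 0.91 | 2.58 | 45.5% | 84.2% |

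The post-operative score alone gives 80.7% throughout.

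At k = 1, varying the correlation:

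| ρ | Power, change | Power, ANCOVA |
|---|---|---|
| 0.1 | 55.9% | 81.1% |
| 0.3 | 66.7% | 84.2% |
| 0.5 | 80.7% | 90.4% |
| 0.7 | 95.5% | 97.7% |

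At k = 0.5 and ρ = 0.5 both variances are 0.75 and there is no loss. A simulation of the four-arm trial (4,000 runs, k = 1), which includes chance baseline imbalance, gave 67.2% for change and 83.1% for ANCOVA at ρ = 0.3, in line with the formula.

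**4. With the family error rate.** Four arms give 4 × 3/2 = 6 pairs. Bonferroni uses 0.05/6 = 0.0083. At k = 1 and ρ = 0.3, power falls to 38% for change and 60% for ANCOVA.

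**5. Under the test actually named.** The z tests compare proportions, so steps 3 and 4 do not describe them directly. With an assumed 1.25 SD effect and k = 1, cutting each variable midway between the two arm means gives 56.0% power for the post-operative score. Change gives 32.3%, 43.1%, 56.0% and 78.2% at ρ = 0, 0.3, 0.5 and 0.7, so break-even stays at 0.5. With unequal cut-offs it moves. It is near 0.4 if the control-arm response is 10% on the post-operative score and 20% on change, and just above 0.6 if it is 30% and 50%.

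**The case against.** The strongest objection is that the plan does not compare mean changes at all. It compares proportions with an undefined cut-off, so the primary test cannot be run as written, and that is a more basic fault than inefficiency. The power figures therefore compare two analyses, neither of which is planned. This stands. It limits what the figures show, but it does not remove the point: choosing a workable test would still leave an unadjusted change score as the variable.

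A reader might infer several stronger things that the documents do not support:
- **That 0.5 is a general threshold.** It requires equal pre- and post-operative SDs. Neither SD is given.
- **That the loss is known to be large.** It runs from nothing (k = 0.5, ρ = 0.5) to very large (k = 1.5). A low correlation is plausible on clinical grounds but is an inference.
- **That the point is independent of the test and the time point.** The break-even moves with the cut-off, and the SDs and correlation depend on which post-operative day or summary is used, which section 4.2.1 does not fix.
- **That the result would be biased.** Arms are randomised, so change from baseline is unbiased. Over-correction concerns chance imbalance only.
- **That patients with little pain before surgery cannot contribute.** Pain can rise after surgery, so a treatment effect can appear as a smaller rise. The post-operative score has the same scale floor.

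**Conclusion.** The point holds as a matter of precision. Section 10.1.2 uses an unadjusted change score, section 4.1 repeats the contrast, and no baseline adjustment is planned anywhere. That adjustment is never less precise than change, apart from one error degree of freedom, holds for any SD ratio and any correlation. How much is lost cannot be settled from the documents. In the illustration at ρ = 0.3 the power deficit is 84.2 − 82.7 = 1.5 percentage points at an SD ratio of 0.5, 84.2 − 66.7 = 17.5 points at 1, and 84.2 − 45.5 = 38.7 points at 1.5. These rest on an assumed 1.3 SD effect, comparison of means and a single pair at 0.05; allowing for six pairs lowers power for both methods. The case for changing the plan is that the gain may be substantial, the cost is almost nil, and the named test has to be restated in any event.

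**What to change.** In section 10.1.2:
- Replace the z tests on change with a linear model (ANCOVA) of one pre-specified post-operative pain summary from the diary, with treatment arm and one named pre-operative score as covariates.
- State which of the two scores in section 7.1.1 is that covariate, for example the holding-area score on the day of surgery. Give that score a distinct label, because section 7.1.1 also uses day 0 for post-operative scoring.
- Report adjusted mean differences with 95% confidence intervals.
- Keep the 0.05 family error rate across the pairwise arm comparisons, for example by Tukey-Kramer or Holm. Make clear that the blanket rule "For all tests, a P value of less than 0.05 will be considered statistically significant" then applies to the adjusted P values for pain.
- Keep change from baseline as a descriptive display.

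Align section 4.1 with this wording. The cost is SAP text and one error degree of freedom; no new data are needed.
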